5.2.4. Systemic and Local PK in Patients with Osteoarthritis of the Knee

Overall, FX006 displayed a favorable plasma PK profile relative to TAcS.

PK observations resulted in a controlled and stable release of TA from PLGA microspheres into synovial tissues, where concentrations remained high relative to plasma concentrations for at least 12 weeks. TA was absorbed systemically, with a plateau in plasma TA concentrations occurring in the first 24 hours post-dose, and slow elimination from the systemic circulation observed in the weeks thereafter.

Relative to TAcS, FX006 32 mg produced substantially lower peak plasma and systemic exposure to TA. FX006 performed as expected, prolonging the residence of TA in the joint while minimizing systemic exposure to TA.

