2.5.2. Pharmacokinetic Variables

Blood samples (4 mL per sample) for TA drug concentration measurements will be obtained from all patients at the following nominal, or planned, times:

- On Day 1, within 1 hour prior to administration of study medication (Nominal Time -1),
- On Day 1, at Hours 1, 2, 3, 4, 5, 6, 8, 10, and 12 (\pm 10 minutes) after injection of the first knee,
- On Day 2, at 24 (\pm 2 hours) after injection of the first knee,
- On Days 8, 15, 29, and 43 (time as convenient during the scheduled visit).

These represent a total of 15 samples from each patient, each sample representing 4 mL of blood, for a maximum estimated total volume of 60 mL of blood collected from each patient for drug concentration measurement.

Procedures for sample collection, handling, storage and shipment will be described in the Laboratory Manual. Plasma TA concentrations will be measured using an established validated LC-MS/MS method.

PK parameter endpoints are described in section 4.8.4.

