4.8.4. Pharmacokinetic analysis

PK analysis will be performed on the PK population. PK parameter estimates will be completed by the study pharmacokineticist and results provided for incorporation into study datasets.

PK parameters will be derived using model-independent methods (non-compartmental analysis (NCA)) as implemented in Phoenix 7, WinNonlin® (version 7) and will be based on TA plasma concentrations from patients in the PK Population. Mean concentration profiles will be computed for each treatment arm: FX006 64 mg and TAcS 80 mg.

Actual sampling times will be used for the estimation of the PK parameters if significant deviations from the nominal sampling time are noted in data review by the study pharmacokineticist. All descriptive summary tables and figures will be presented with the nominal (planned) sampling times.

All blood samples will be assayed for concentration levels of TA using a validated High Performance Liquid Chromatographic Method with Tandem Mass Spectrometry Detection method (LC/MS-MS), each matrix with a validated assay range in pg/mL. Bioanalytical methods for the assay of TA will be provided in a separate bioanalytical report that will include information on calibration standards for the assay.

Each PK parameter will be estimated for each patient with NCA methodology.

The PK endpoints to be computed on plasma TA concentration measurements will be either observed from those concentration measurements or estimated by WinNonlin® (version 7) using the trapezoidal rule for calculation of the AUC estimates to the last measureable concentration. Additional estimates of the half-life, clearance, residence time, volume of distribution and the extrapolated area for the $AUC_{0-\infty}$ and related parameters will be estimated using the slope estimate for the terminal elimination rate constant for each patient with WinNonlin® (version 7).

PK variables consist of PK parameters identified in Table 2.

Table 2 PK Parameters

PK Parameter	Description (Computation Method)
C_{max}	Peak exposure, Maximum plasma concentration observed.
t_{max}	Time from dosing to peak exposure, time to maximum plasma concentration observed.
C_{last}	Last quantifiable plasma concentration (last value observed above assay BLOQ)
t_{last}	Time of last quantifiable plasma concentration
λ_z	Terminal elimination rate constant (lambda_z)
$t_{1/2}$	Terminal half-life: Computed as $t_{1/2} = \frac{Ln(2)}{\lambda_z}$

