$AUC_{(0-t)}$	Exposure: Area Under the Plasma Curve from time 0 to the last quantifiable concentration (t). Calculated using the linear trapezoidal rule.
$AUC_{(0-24)}$	Exposure: Area Under the Plasma Curve from time 0 to 24 hours post IA injection. Calculated using the linear trapezoidal rule
$AUC_{(0-\infty)}$	Exposure: Area Under the Plasma Curve from time 0 extrapolated to infinity. Calculated as follows: $AUC_{inf} = AUC_{(0-t)} + \frac{C_{last}}{\lambda_z}$ where C_{last} is the last quantifiable concentration.
CL	Total Body Clearance, computed as Dose/ $AUC_{(0-\infty)}$
MRT	Mean residence time extrapolated to infinity, computed as $AUMC_{(0-\infty)}/AUC_{(0-\infty)}$
Vz_F	Volume of Distribution, based on terminal phase, computed as : $\frac{Dose}{\lambda_z \cdot AUC_{(0-\infty)}}$

Descriptive summaries of the individual patient PK parameters and population summaries over all patients will be presented. Individual linear-linear and log-linear concentration profiles will be completed for each patient. Graphical display (plasma drug concentration curves) will be used to present geometric mean with 95% CIs for plasma drug concentrations (linear-linear and log-linear plots) for each treatment arm.

All PK parameters and data will be presented in a data listing. Results from the PK analysis will be included in the CSR. Along with the bioanalytical report from the assay laboratory, model output from the NCA analysis will be provided in a separate document.

A linear model will be used to compare the PK parameters from extended-release FX006 and immediate-release TAcS for each C_{max} , T_{max} , C_{last} , MRT, and AUC parameters. The model will include treatment as a single fixed effect. The least square mean difference (LSMD) between the two treatments will be explored to examine the magnitude of difference in exposure PK parameters between FX006 and TAcS. All p-values will be considered informative.

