4.8.5. Exploration of Bioequivalence between FX006 and TAcS

Bioequivalence (BE) ratios between extended-release FX006 (Test) and immediate-release TAcS (Reference) for C_{max} and AUC parameters will be explored. Bioequivalence between Test and Reference will be evaluated using the average BE method for the mean ratio between test and reference products ($\mu T / \mu R$) as described in FDA guidance for the assessment of bioequivalence (FDA, 2013).

The FDA Guidance on the assessment of Bioequivalence recommends that bioequivalence measures of AUC and C_{max} be log-transformed. In this study, the natural log will be used to transform the values for the model, and the C_{max} , AUC_{0-24} , and $AUC_{0-\infty}$. PK parameters will be exponentiated from a mixed effects model to examine bioequivalence.

In this study bioequivalence is not expected for the ratio of FX006 / TAcS. The properties of FX006 suggest that a reduced C_{max} (reduced maximum exposure) is evident due to slower release of TA into systemic circulation. The potential shift in T_{max} and potential decay in C_{max} , both of which would be associated with corresponding differences in AUC will be explored.

A linear mixed effects model may be used for this study to average bioequivalence with PK parameters of log-transformed AUC_{0-24} , $AUC_{0-\infty}$, and C_{max} . In the initial model fixed effects for treatment and site will be included, with a random effect for patient.

GM with 95% CIs will be presented for each treatment group. BE ratio with standard error (SE) and 90% CIs will be presented for C_{max} , AUC_{0-24} , and $AUC_{0-\infty}$.

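### The planned Tmax comparison is a difference in mean hours from a linear model, which a single late peak could distort; a rank-based comparison would be a cheap improvement

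*SAP*

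**What the plan says.** SAP 4.8.4 has one sentence on the between-arm comparison: "A linear model will be used to compare the PK parameters from extended-release FX006 and immediate-release TAcS for each" of Cmax, Tmax, Clast, MRT and the AUC parameters. It continues: "The model will include treatment as a single fixed effect". On the effect measure it says: "The least square mean difference (LSMD) between the two treatments will be explored". On the tests it says: "All p-values will be considered informative".

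No transformation or rank method is given for Tmax. Log transformation appears only in SAP 4.8.5, for Cmax and AUC.

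Table 2 of the SAP defines Tmax as "Time from dosing to peak exposure, time to maximum plasma concentration observed". SAP 2.5.2 schedules post-dose samples at 1, 2, 3, 4, 5, 6, 8, 10 and 12 h and at 24 h. After that come only four visits: "On Days 8, 15, 29, and 43 (time as convenient during the scheduled visit"). Under SAP 4.8.4, actual times replace nominal ones only if the pharmacokineticist notes significant deviations.

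Protocol 5.2.4 describes FX006 "with a plateau in plasma TA concentrations occurring in the first 24 hours post-dose", and then a slow fall over the following weeks. SAP 4.8.5 names a possible shift in Tmax and a lower Cmax, "both of which would be associated with corresponding differences in AUC will be explored".

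**The concern.** A linear model with treatment as its only term is the equal-variance two-sample t comparison, here on raw hours. That scale suits Tmax poorly. Up to 24 h the possible values are a few hours apart, and the next nominal value is seven times larger. On a flat plateau, which sample happens to be highest depends partly on assay and sampling variation. If one patient's highest sample were the Day 8 one, that patient would dominate both the arm mean and the pooled standard deviation.

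At stake is how the Tmax shift is described, which the SAP says it will explore. With about 12 patients per arm, one value could enlarge the estimated shift and also remove its nominal significance.

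**Working it through.** The documents give no effect size, power or variability for Tmax, so there is no figure of the plan's own to reproduce. The sample size statement concerns exposure ratios only.

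**Inputs from the documents**
- 12 patients per arm, with a 10% loss allowed for (SAP 4.1.2), so about 11 evaluable.
- Nominal post-dose times 1–6, 8, 10, 12, 24, 168, 336, 672 and 1008 h (SAP 2.5.2; Day 8 = 7 × 24 = 168 h, and so on).
- Visits from Day 8 on may move by 2 days (SAP Table 1, footnote 2), so Day 8 spans 168 ± 48 = 120 to 216 h.

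**Step 1. Leverage of one patient, whatever the other data.** Moving one FX006 value from 24 h to time t changes the mean difference by (t − 24)/n.
- n = 12, t = 168: 144/12 = 12.0 h.
- n = 11, t = 168: 144/11 = 13.1 h.
- n = 12 across the Day 8 window: (120 − 24)/12 = 8 h to (216 − 24)/12 = 16 h.

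**Step 2. Illustration with assumed values on the grid.** These are not trial data.
- TAcS: 2, 3, 4, 4, 5, 5, 6, 6, 8, 8, 10, 12 h (mean 6.08, variance 8.63, median 5.5).
- FX006: 6, 8, 8, 10, 10, 12, 12, 12, 24, 24, 24, 24 h (mean 14.50, variance 52.45, median 12).

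Linear model: difference d; pooled SD s = √[(variance 1 + variance 2)/2]; SE = s√(2/12); t on 22 df.

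No late peak: d = 14.50 − 6.08 = 8.4; s = √[(52.45 + 8.63)/2] = 5.53; SE = 2.26; t = 3.73.

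One 24 h value moved to 168 h: FX006 mean 26.50, variance 2029.2; d = 20.4; s = 31.9; SE = 13.0; t = 1.57.

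| FX006 patients at Day 8 | Mean difference (95% CI), h | p | Hodges-Lehmann shift, h | Rank-sum p |
|---|---|---|---|---|
| 0 | 8.4 (3.7 to 13.1) | 0.001 | 6.0 | 0.001 |
| 1 | 20.4 (−6.6 to 47.4) | 0.13 | 6.0 | 0.001 |
| 2 | 32.4 (−4.0 to 68.8) | 0.08 | 6.0 | 0.001 |

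The FX006 median is 12 h in all three rows. Allowing unequal variances does not help the one-patient row (p = 0.15).

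**Step 3. Different assumed data.** TAcS 2, 3, 3, 4, 4, 5, 5, 6, 6, 6, 8, 8 h; FX006 4, 5, 6, 6, 8, 8, 10, 10, 12, 12, 24, 24 h. The mean difference is 5.8 h (1.6 to 9.9; p = 0.009). With one 24 h value moved to 168 h it becomes 17.8 h (−9.8 to 45.3; p = 0.20). The Hodges-Lehmann shift is 4.0 h (1.0 to 7.0; p = 0.005) both times.

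**Step 4. How likely is a late peak?** The documents do not say. As a range, assume a profile flat from 5 to 24 h, log-normal sampling variation of 15% or 25%, and a Day 8 mean set at a fraction of the plateau. If p is the simulated chance that one patient peaks at Day 8 or later, the chance of at least one in 12 is 1 − (1 − p)^12.

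| Day 8 mean, % of plateau | At least one of 12 |
|---|---|
| 90 | 39–58% |
| 80 | 8–29% |
| 70 | 1–9% |
| 60 or lower | 0–2% |

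**The case against.** The case against acting is substantial.

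- **The late peak is hypothetical.** A reader might infer from the plateau that some FX006 patients will peak at Day 8. The documents do not support that. None reports such a patient, and Protocol 5.2.4 goes on from the plateau to slow elimination. Step 4 gives an appreciable chance only if Day 8 concentrations remain close to the plateau. This stands.
- **Without a late peak the methods agree.** The first row of the Step 2 table gives the same direction and the same p-value either way. This stands for that example.
- **Much of the protection is already planned.** Protocol 9.4.5 and SAP 4.2.1 provide the median, minimum and maximum by arm, and SAP 4.8.4 provides individual listings and profiles. A reader of the report would see medians of 12 h and 5.5 h beside a distorted mean. This stands, but these are descriptive: no median- or rank-based comparison between arms is planned.
- **No decision rests on Tmax.** SAP 4.1.1 names Cmax and two AUCs as the key parameters, and the Tmax p-values are informative only. This stands and limits the weight of the point.
- **Tmax need not take only scheduled values, and no interval is promised for the mean difference.** Actual times may be used, and SAP 4.2.1 makes 95% CIs optional. Both are correct. The gap between 24 h and Day 8 remains, and the sensitivity applies equally to the standard error and p-value.
- **A late maximum could be real.** For an extended-release product it would be part of the release profile. The Hodges-Lehmann shift stayed fixed partly because the example moved values that were already the largest. This stands, and is why late peaks should be counted as well.

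None of this shows that a difference in mean hours is the better summary of Tmax.

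**Conclusion.** The point holds as a minor one. The planned Tmax comparison is sensitive to any single late peak: with 12 per arm, one FX006 patient moved from 24 h to a nominal Day 8 peak adds 12 h to the difference, and this needs no further assumption. The change from 8.4 h (p = 0.001) to 20.4 h (p = 0.13) rests on assumed data; a second assumed set shows the same pattern.

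Two stronger readings are tempting. One is that the trial's Tmax result will be distorted; that would require a Day 8 peak, which the documents neither report nor lead one to expect. The other is that the PK conclusions are at risk. The Cmax and AUC results do not depend on Tmax, and no success criterion involves it. The change is therefore optional, or at most a mild recommendation.

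**What to change.** In SAP 4.8.4, remove Tmax from the linear-model list. Compare arms by the Hodges-Lehmann difference with its 95% CI and a Wilcoxon rank-sum test, shown beside the medians and ranges already planned. Give the number of patients per arm whose Tmax falls at Day 8 or later, so that the rank method does not hide a true late peak.

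The cost is a sentence or two in the SAP and a row or two in a table; no new data are needed. The drawbacks are slightly lower efficiency if Tmax happens to be near normal, and insensitivity to how late a late peak is, which the count partly offsets.

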9.4.5. Pharmacokinetic Analysis

Pharmacokinetic (PK) parameters will be derived for each patient from plasma concentrations of TA using model-independent non-compartmental analysis: (NCA) [Phoenix 7, WinNonlin® 7]. Individual elapsed sampling times (actual time) will be used in the PK calculations if significant deviations from the nominal sampling times are noted, otherwise nominal times will be used for analysis. Complete details on the calculation of PK parameters, and handling of concentration values below the LLOQ will be fully specified in the SAP.

Descriptive summaries of the TA plasma concentration levels (ng/mL) observed at each nominal time point will be provided for FX006 and TAc treatments. Descriptive summaries of the PK parameter estimates from each treatment group will also be completed. Summary statistics for continuous variables will include n, mean, standard deviation, coefficient of variation (CV%), median, minimum, and maximum, geometric mean and standard error of the geometric mean.

By patient plots (linear-linear, log-linear) of the plasma TA concentration data will be completed for each treatment group.

The PK parameters for C_{max} , T_{max} , AUC, and MRT PK parameters will be informative of the overall systemic exposure of TA from extended-release FX006 and immediate-release TAc. A linear model will be used to compare the PK parameters from extended-release FX006 and immediate-release TAc. Full details of the linear model will be specified in the SAP.

Bioequivalence (BE) ratios between extended-release FX006 (Test) and immediate-release TAc (Reference) for C_{max} and AUC parameters will be explored. Bioequivalence between Test and Reference will be evaluated using the average BE method for the mean ratio between test and reference products ($\mu T / \mu R$) as described in FDA guidance. Full details on the analysis of BE will be included in the SAP.

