4. STATISTICAL METHODS

4.1. Sample Size Justification

4.1.1. Sample Size Considerations

In this study, it is expected that the systemic exposure in plasma of TA from extended-release FX006 should not exceed that of the immediate-release TAcS formulation for the key parameters of C_{max} , $AUC_{(0-t)}$, and $AUC_{(0-inf)}$.

In a previous PK study with knee OA patients (FX006-2015-009) the ratio of the mean exposure parameters for FX006 32 mg (N=60) and TAcS 40 mg (N=18) for C_{max} was 0.10 with the upper limit of its 90% CI being 0.15 and for $AUC_{(0-inf)}$ was 0.52 with the upper limit of its 90% CI being 0.86. The pooled coefficients of variation for the parameters was between 0.53 (C_{max}) and 0.68 (AUC_{0-inf}).

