4.1.2. Sample Size Estimate

In this study, it is expected that the ratio of exposure means (FX006/TAcS) will be less than 1.0 when administered to treat bilateral knee OA. A sample size of 12 in each treatment arm (24 in total) is estimated. The sample size of 24 achieves approximately 90% power, with a two-sided alpha 0.05, to detect a ratio less than 1.0 of the exposure PK parameter means (FX006 / TAcS), with a pooled coefficient of variation estimate of 0.68 (PASS 15 Power Analysis and Sample Size Software (2017). NCSS, LLC. Kaysville, Utah, USA, ncss.com/software/pass). The sample size of 12 per treatment arm assumes a 10% noncompliance sampling rate (a drop-out rate) for providing complete blood samples for PK analysis, and is sufficient to characterize the comparative PK of FX006 and TAcS in this study. The total sample size is estimated to be 24 patients (12 in each treatment arm) for the study.

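### SAP 4.8.4 compares exposure by a mean difference with no log scale or ratio, although the trial is planned on an FX006/TAcS ratio; the 4.8.5 ratios carry only 90% intervals and omit AUC(0-t)

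*SAP*

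**What the plan says.** **Planning.** SAP 4.1.1 expects that FX006 exposure "should not exceed that of the immediate-release TAcS formulation for the key parameters of" Cmax, AUC(0-t) and AUC(0-inf). SAP 4.1.2 claims about 90% power at two-sided 0.05 "to detect a ratio less than 1.0 of the exposure PK parameter means (FX006 / TAcS"), with a pooled CV of 0.68. Protocol 9.3 says the same, and Protocol 9.2 sets two-sided intervals and tests at 0.05.

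**The comparison.** Protocol 9.4.5 defers: "Full details of the linear model will be specified in the SAP". SAP 4.8.4 is where that model appears. Treatment is its only term, and it is applied to Cmax, Tmax, Clast, MRT and the AUC parameters. On the estimate it says: "The least square mean difference (LSMD) between the two treatments will be explored to examine the magnitude of difference in exposure PK parameters". Then: "All p-values will be considered informative". It gives no transformation, ratio or interval level for the comparison; log-linear in that section describes plots only.

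**The bioequivalence section.** SAP 4.8.5 does use logs: "In this study, the natural log will be used to transform the values for the model". Its opening sentence speaks of AUC parameters in general, but each specific list names only Cmax, AUC(0-24) and AUC(0-inf). Ratios are to be shown with a standard error and a 90% interval (Table 14.2.2). The 95% intervals there are for each arm's geometric mean. On the model: "A linear mixed effects model may be used for this study to average bioequivalence with PK parameters of log-transformed" AUC(0-24), AUC(0-inf) and Cmax; and "In the initial model fixed effects for treatment and site will be included, with a random effect for patient". SAP 4.2.4 plans no formal covariate adjustment, and SAP section 5 declares only a change in listing order.

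**The concern.** Primary objective (a) is a comparison of exposure, and the plan frames it as a ratio. The section that delivers the comparison gives a difference, so its estimate is not on the planning scale. If it is run on untransformed values, as it reads, it also loses power for AUC, where the data are skewed and the spread grows with the mean.

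Section 4.8.5 repairs this only in part. For AUC(0-t), a key parameter, the mean difference remains the only specified between-arm estimate. For Cmax and AUC(0-inf) a ratio is reported, but without the 95% interval that corresponds to two-sided 0.05. A reader who sees a 90% upper limit below 1.0 may conclude that exposure is lower when the planned level would not support that.

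The 4.8.5 model is itself unsuitable as the source of the ratio. Each patient contributes one value per parameter, so a random patient effect cannot be separated from the residual. The site term conflicts with SAP 4.2.4. The two sections thus offer two models for one comparison, with different terms and apparently different scales.

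**Working it through.** **Inputs.** From SAP 4.1.1 and 4.1.2: CV 0.68 for AUC(0-inf) and 0.53 for Cmax; earlier single-knee ratios 0.52 for AUC(0-inf) and 0.10 for Cmax; 12 per arm; 10% sampling loss, so about 11 per arm; two-sided 0.05. Assumptions: log-normal data and equal CV in both arms. The bilateral ratio is unknown, so 0.52, 0.60 and 0.70 are shown.

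**The plan's own figure.** Log SD = sqrt(ln(1 + 0.68²)) = 0.617. Standard error of the log ratio at 12 per arm = 0.617 × sqrt(2/12) = 0.252. At ratio 0.52, |ln 0.52| / 0.252 = 0.654 / 0.252 = 2.60, which gives two-sided power of 74% (normal) or 70% (noncentral t, 22 df). The stated 90% is not reproduced. The plan does not state its assumed ratio; 90% would need a true ratio of about 0.43 to 0.44. That is a separate point and does not affect what follows.

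**Power, untransformed v log.** 200,000 simulated trials per scenario, pooled-variance t-test, two-sided 0.05, CV 0.68:

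| True ratio | 12/arm: raw | 12/arm: log | 11/arm: raw | 11/arm: log |
|---|---|---|---|---|
| 0.52 | 62% | 70% | 57% | 66% |
| 0.60 | 42% | 49% | 39% | 46% |
| 0.70 | 23% | 27% | 21% | 25% |

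At ratio 1.0 the untransformed test rejects in 4.3% of trials, so its size is kept. For Cmax (ratio 0.10, CV 0.53) power is near 100% on either scale.

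**Interval level.** The upper limit falls below 1.0 when the observed ratio is below exp(−t × 0.617 × sqrt(2/12)), taking the observed SD as the planned one.
- 90% interval, 22 df, t = 1.717: threshold 0.649.
- 95% interval, 22 df, t = 2.074: threshold 0.593.
- With treatment and four balanced sites (19 df): 0.647 and 0.590.

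An observed ratio between 0.593 and 0.649 therefore clears 1.0 at 90% but not at 95%. The simulated share of trials with a 90% limit below 1.0 and a 95% limit not below it is 10.9%, 13.4% and 12.0% at true ratios 0.52, 0.60 and 0.70 (12 per arm).

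**Random patient effect.** One simulated set of 24 patients with one record each was fitted with treatment and site fixed and patient random. The REML log-likelihood (2.7177), treatment estimate (−0.8011) and standard error (0.1695) are identical whether the patient effect is given 0, 10, 50, 90 or 99.9% of the variance. The data hold no information on that term, and the software warns of a Hessian that is not positive definite.

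**The case against.** The strongest reply is that most of the remedy is already planned. SAP 4.8.5 commits to the log transform and to ratios for Cmax, AUC(0-24) and AUC(0-inf), with a dedicated table; its conditional wording qualifies the mixed model, not the ratios. That stands, and it narrows the concern to AUC(0-t), the interval level and the 4.8.4 estimate.

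Second, nothing formal depends on this. The difference is to be explored, p-values are informative, and neither document makes an upper limit below 1.0 a success criterion. A mean difference below zero and a ratio of means below one point the same way. This stands too, and it limits the weight of the finding. The power loss and the 11% to 13% of trials bear on how results would be read.

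Third, SAP 4.8.4 is silent on scale; it does not prescribe untransformed values. True, so the raw-scale figures are conditional on that reading. But the protocol left the model's full details to the SAP, and the scale is one of them.

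Fourth, 90% intervals are usual for average bioequivalence, the earlier study is quoted with 90% limits, and a 95% interval could be derived from the standard error. Likewise, an AUC(0-t) ratio could be worked out from each arm's geometric mean and its variability. Derivable is not planned, and per-arm summaries are not a between-arm estimate.

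Fifth, the redundant patient effect changes neither the estimate nor its standard error. Correct; the objection to it is that it is uninformative and invites fitting problems, not that it biases the result.

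**Conclusion.** The concern holds. The SAP's linear-model comparison for primary objective (a) is not on the ratio scale used for planning, AUC(0-t) has no specified ratio, and no ratio has a planned 95% interval. Under log-normal data with CV 0.68 in both arms, an untransformed analysis gives up about 4 to 8 percentage points of power for AUC at 12 per arm over true ratios 0.70 to 0.52. The choice of 90% rather than 95% would change whether the upper limit excludes 1.0 in about 11% to 13% of trials. Cmax conclusions are unaffected at the earlier ratio of 0.10. Type I error is not inflated and no formal decision rule breaks. It should be fixed because a better analysis is available at almost no cost. Moving to the log scale does not restore the stated 90% power.

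**What to change.** - In SAP 4.8.4, fit the treatment-only linear model to ln(Cmax), ln(AUC(0-t)), ln(AUC(0-24)) and ln(AUC(0-inf)). Report the geometric mean ratio FX006/TAcS with its two-sided 95% interval and p-value. Keep the untransformed mean difference as descriptive.
- In SAP 4.8.5 and Table 14.2.2, add AUC(0-t), take the ratios from this same model, and show the 90% interval for the bioequivalence display beside the 95% interval.
- Replace the mixed-model sentences in 4.8.5 rather than making that model mandatory. If a site effect is wanted, name it as a sensitivity analysis and reconcile it with SAP 4.2.4.

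The cost is wording in two SAP sections and one changed table. No new data are needed.
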